2.2 Primary Study Endpoints

Each complication will be documented for every patient. The rates of complication will be analyzed individually for each technique, and risk ratios will be conducted between techniques to determine which technique has the lowest risk of developing a complication. Complications include infection, abscess formation, dehiscence, prolonged drainage, allergic reactions, among others.

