2.4 Inclusion Criteria

Following IRB approval, all patients who are scheduled for joint arthroplasty at NYULMC will be eligible to take part in this research study. Inclusion criteria includes:

- All patients ≥ 18 years of age treated with joint replacement surgery at our institution
- Patients who are willing to participate in post-operative surveys

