2.5 Exclusion Criteria

- Treatment of total joint replacement surgery at an outside institution
- Patients younger than 18
- Pregnant women, prisoners, adults unable to consent.

Vulnerable Subjects: No vulnerable subjects will be included within this study

CONFIDENTIAL

This material is the property of the NYU School of Medicine and Langone Medical Center. Do not disclose or use except as authorized in writing by the study sponsor

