3.4 Blinding of Study Product

Given the nature of the application of the wound closure device, which will be visible to the surgeon at the time of application and the patient postoperatively, the study will not be blinded to either the surgeon or the patient. Prior to discharge, a blinded plastic surgeon will be asked to assess the wound based on comessis and overall quality of wound healing.

4 Study Procedures

Patients who are eligible for the study will be notified on a preoperative visit via a tool on the electronic medical record system (Epic).

At this time, surgeon research assistant will ask the patient if they would like to be involved in the study. If consent to participate in the study is given, the surgeon will go ahead with the randomization process, which will dictate what type of wound closure device will be used at the time of the surgery. All of the wound devices are currently being used at the institution. The study will follow normal standard of care for the application of these devices. The only different will be the randomization process that will take place prior to the surgery. Data will be collected regarding the primary outcomes at the time of discharge as well as at their normally scheduled postoperative visits. Patients will be followed up to their 3rd postoperative visit. Prior to discharge, a plastic surgeon, who will be blinded to the type of wound closure technique that the patient received, will assess the wound for the quality of wound healing. At their postoperative visits, the physician will document whether a complication had occurred. Patients will also be given patient-reported outcome questionnaires, including VAS scores and HWES, that will measure the level of satisfaction of their wound healing at the time of these visits.

The following table shows the visits and procedures/ observational data collection that will occur during the study:

Activity	Pre-operative assessment	Date of surgery	Prior to discharge	Postop visit #1	Postop visit #2	Postop visit #3
Study team procedures						
Consent	X					
Medical History	X			X	X	X
Physical Exam	X		X	X	X	X
Height	X			X	X	X
Weight	X			X	X	X
Vitals signs	X		X	X	X	X
Record of			X	X	X	X

CONFIDENTIAL

This material is the property of the NYU School of Medicine and Langone Medical Center. Do not disclose or use except as authorized in writing by the study sponsor

complications						

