5.1 Sample Size Determination

Based on an 80% power analysis, incidence rates reported from past studies, and a ratio of 1:1:1 cohort size between the different treatment groups involved, a total of 200 patients will be included in the study. Given an estimated 700 total hip and knee replacements done in a quarter each year at NYULMC, the project is scheduled to take a total of 7 months. It is estimated that 50% of all patients will be approached to be consented

from these 700 patients (a total of 350 patients will be enrolled to reach the target number of participants), and an estimated 60% of these patients will agree to follow through with the study.

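### Eligibility does not exclude an operative site that is already infected, open or draining, so persistent or recurrent infection can count as a primary-endpoint event of the skin-closure technique

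*Combined protocol and SAP*

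**What the plan says.** - **Who enters.** Section 2.4 says that "all patients who are scheduled for joint arthroplasty at NYULMC will be eligible to take part in this research study", and its first criterion is "All patients ≥ 18 years of age treated with joint replacement surgery at our institution". Neither statement refers to the indication, to primary or revision surgery, or to the state of the operative site.
- **Who is kept out.** Section 2.5 lists "Treatment of total joint replacement surgery at an outside institution", age under 18, and "Pregnant women, prisoners, adults unable to consent". Nothing there concerns infection, an open wound or drainage.
- **What is counted.** Section 2.2 says "Each complication will be documented for every patient" and "Complications include infection, abscess formation, dehiscence, prolonged drainage, allergic reactions, among others". Section 5.2 repeats this. No component is defined, and there is no rule on onset or attribution.
- **How it is recorded.** Section 4 says "At their postoperative visits, the physician will document whether a complication had occurred". In its visit table, complications are recorded from the pre-discharge assessment onward. Medical history and physical examination are recorded before surgery.
- **Preexisting conditions.** Section 6.1 has clinically significant abnormalities at screening recorded as preexisting, and counts them as adverse events only if they worsen. It governs adverse events and is not linked to the endpoint in 2.2.

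**The concern.** The primary objective in 1.4 is the complication rate that goes with each closure technique. An infection that led to the operation, and then persists or comes back, is an event of the underlying disease. It would occur whichever device closed the skin. If such patients enter and their events are counted, the absolute rates rise in every arm, the contrast between arms shrinks, and a few patients falling unevenly across arms of about 67 can shift an estimate that rests on few events. The same patients can also affect length of stay, readmission and length of operation, which feed the cost comparison in 1.4 and 2.3.

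**Working it through.** **Text check**

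1. Take an adult scheduled at this institution for revision of a joint implanted here, because of infection. The general statement and the first criterion of 2.4 are met, and willingness to complete surveys is a separate matter.
2. Go through 2.5. The operation is not at an outside institution, and the patient is not under 18, pregnant, a prisoner or unable to consent. No exclusion applies.
3. The outside-institution line does not close the gap on either reading. If it means the index operation, it repeats 2.4. If it means any earlier replacement, it removes revisions of joints implanted elsewhere but keeps revisions of joints implanted here.
4. Infection or abscess found after the operation falls under the list in 2.2. Nothing in 2.2, section 4 or 5.2 requires comparison with the preoperative state.
5. The preoperative history and examination would show the infection, but no section uses them to exclude, stratify, adjust or define an event. Section 5.2 plans multivariate analysis without naming covariates.

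**Size, on assumptions**

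From the documents: 200 patients, allocated 1:1:1, so 200/3 = 66.7 per arm. Section 5.1 gives no event rates, alpha or effect size, so the figure of 200 can be neither reproduced nor refuted. It also gives no share of revision or infected cases. Everything below is assumed.

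*Event count.* With a share of 1-2%, 200 × 0.01 = 2 and 200 × 0.02 = 4 patients. With a 5% event rate, 200 × 0.05 = 10 events. The addition is 2/10 = 20% to 4/10 = 40%. This is an upper figure, since it supposes that every such patient is counted.

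*Dilution.* If a share f is always counted, an arm with true rate p shows f + (1 − f)p. From a 5% control rate, 80% power is not reachable at 66.7 per arm, so the loss is illustrated at 20% v 5%, where the trial has some power. Power is for a two-sided 5% test, Φ[(|d| − 1.96·SE0)/SE1], where d is the difference in rates and SE0 and SE1 are its pooled and unpooled standard errors.

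| f | such patients in 200 | rates shown | risk ratio | power |
|---|---|---|---|---|
| 0 | 0 | 20.0% v 5.0% | 0.25 | 75.1% |
| 1% | 2 | 20.8% v 5.95% | 0.29 | 71.7% |
| 2% | 4 | 21.6% v 6.9% | 0.32 | 68.4% |
| 5% | 10 | 24.0% v 9.75% | 0.41 | 59.5% |
| 10% | 20 | 28.0% v 14.5% | 0.52 | 47.8% |

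*Chance imbalance.* With k such patients allocated independently and equally to three arms, the probability that some two arms differ by at least two of them is:
- k = 2: 1/3 = 33%
- k = 3: 1 − 6/27 = 78%
- k = 4: 1 − 36/81 = 56%

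A difference of two at a 5% rate means, for example, 67 × 0.05 = 3.35 events in one arm and 5.35 in another: 5.0% v 8.0%, risk ratio 1.6. The standard deviation of the count in one arm is √(67 × 0.05 × 0.95) = 1.8, so two events is about one standard deviation. The two-sample test of 5.35 v 3.35 of 67 gives p of about 0.48.

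**The case against.** The strongest reply is that the plan already means new events. The title concerns wound complications after surgery, 2.2 speaks of the risk that a complication develops, and recording starts only after the operation. The component is prolonged drainage, which in a list of closure complications reads naturally as drainage from the new wound. This largely stands. A reader might infer that the plan intends to count the infection present at entry, or that any preoperative drainage is an endpoint event, and the documents support neither. What remains is that a new-onset reading is not written as a rule, and that even a strict one leaves in recurrence of the infection that prompted the operation.

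A second reply is that infected revisions are inferred from silence. It is true that revisions are not named in the eligibility text, and their share could be near zero. But 2.4 is an affirmative rule that takes all scheduled arthroplasty, so admission follows from its wording.

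A third reply is that random allocation balances such patients. On average it does, which is why dilution is the main effect. The balance is less assured with about 67 per arm and the alternating assignment described in 3.2, but that assignment is a separate matter.

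A reader might also infer that the trial should be limited to primary hip or knee surgery because 5.1 counts that population. Section 5.1 bases its estimate on "Given an estimated 700 total hip and knee replacements done in a quarter each year at NYULMC" and does not separate primary from revision. Limiting entry in that way is a choice of target population, not a correction.

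**Conclusion.** The point holds in this form: 2.4 and 2.5 let a re-operation for infection enter, and 2.2 lets persistent or recurrent infection or abscess count against the closure technique. This rests on the text and needs no assumption. The size does. At a 1-2% share and a 5% event rate, about 2-4 events would be added to roughly 10, and at assumed rates of 20% v 5% power would fall from 75.1% to between 71.7% and 68.4%. The expected effect is mainly dilution, with chance imbalance possible.

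A reader might infer from the risk ratio of 1.6 that these patients would create a false difference between devices. The documents do not support that. The figure supposes a particular imbalance on top of two assumed rates, and it lies within ordinary chance variation for arms of this size. Nor does anything in the text show that one device would be favoured over another.

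**What to change.** - **2.5:** add an exclusion for active or suspected infection, open wound or drainage at the operative site at entry. This is the main change, because it also removes recurrences, which an onset rule alone would leave in.
- **2.2 (and its repeat in 5.2):** count only complications with onset after skin closure, judged against the preoperative history and examination that section 4 already collects.
- **If other revisions remain eligible:** record primary or revision for each patient, and in 5.2 either adjust for it or report a sensitivity analysis without revisions. Restriction to primary surgery is optional.
- **Separate wording matter in 2.5:** say whether the outside-institution line refers to the index operation or to any earlier replacement.

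The cost is a few lines of text, one additional recorded item if revisions stay in, and a slightly smaller eligible pool, so accrual might run slightly longer.

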3.2 Method for Assigning Subjects to Treatment Groups

Names of patients who are consented for the study will be inputted into a computer and randomized to one of the three treatment groups based on an alternating method. A randomized control trial will provide the highest level of evidence without altering the potential risks to the patient as all three wound closure techniques have been found to have comparable complication rates.

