5.2 Statistical Methods

Data on patient baseline characteristics, procedural characteristics, perioperative outcomes, functional outcomes, and costs will be collected. Single variable and multivariate statistical analysis will be performed to assess the aforementioned data points. Dichotomous data outcomes will be analyzed using odd ratios and chi-squared tests while continuous data points will be analyzed using Student t-tests. Each complication will be documented for every patient. The rates of complication will be analyzed individually for each technique, and risk ratios will be conducted between techniques to determine which technique has the lowest risk of developing a complication. Complications include infection, abscess formation, dehiscence, prolonged drainage, allergic reactions, among others. Cost effectiveness will be determined by the differences in quality metrics such as LOS, readmissions, cost of supplies, and differences in wound closure time between the different wound closure techniques. Each of these variables will be calculated based on the associated hospital costs and analyzed to determine the most cost effective wound closure technique.

CONFIDENTIAL

This material is the property of the NYU School of Medicine and Langone Medical Center. Do not disclose or use except as authorized in writing by the study sponsor

6 Safety and Adverse Events

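### Joint type is neither an allocation stratum nor a named covariate: a cheap precision gain for the time and length-of-stay outcomes, minor for the complication endpoint

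*Combined protocol and SAP*

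**What the plan says.** - **Population.** Section 2.4 includes "All patients ≥ 18 years of age treated with joint replacement surgery at our institution". Section 5.1 bases its accrual estimate on "700 total hip and knee replacements done in a quarter". It does not split that figure by joint, and it does not say whether other joints are expected.
- **Allocation.** Under section 3.2 patients are "randomized to one of the three treatment groups based on an alternating method". No stratification factor is named.
- **Size.** Section 5.1 gives "a ratio of 1:1:1 cohort size between the different treatment groups involved" and states that "a total of 200 patients will be included in the study", with 80% power. It reports no complication rate, target difference or alpha.
- **Analysis.** Section 5.2 states: "Dichotomous data outcomes will be analyzed using odd ratios and chi-squared tests while continuous data points will be analyzed using Student t-tests". Sections 2.2 and 5.2 add complication rates by technique and risk ratios between techniques. Section 5.2 also says that procedural characteristics will be collected and that single-variable and multivariate analyses will be done. It names no covariate or model, and it does not say whether the multivariate results bear on the primary comparison.
- **Time and cost.** Sections 1.4, 2.3 and 5.2 build the cost-effectiveness objective on supply costs, operation length, closure time, length of stay, readmissions and complications.

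**The concern.** Which joint is replaced is known before surgery. It could plausibly affect wound complications, closure time, operative time and length of stay. If it does, and it is neither balanced by design nor used in the analysis, two things follow. Chance differences in joint mix move the estimated differences between techniques, and variation due to joint stays in the error term. With three arms of about 67, noticeable chance differences in mix are to be expected. The unspecified multivariate analysis also leaves the choice of adjustment open until the data have been seen. At stake is mainly precision on the time and length-of-stay outcomes, and a comparison that can be read without asking which arm had more knees.

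**Working it through.** **The plan's own figure.** 200 / 3 = 66.7, so about 67 per arm. The total of 200 cannot be reproduced, because section 5.1 gives no rates, difference or alpha. For orientation, 67 per arm at 80% power (two-sided 0.05 assumed, no continuity correction) corresponds to about 5% v 21% or 10% v 29%.

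**Assumed inputs, not in the documents:** hip/knee mix 50:50; independent random allocation; risks by joint as tabulated; share of continuous-outcome variance explained by joint (R²) of 10% to 30%.

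**Step 1: chance imbalance.** SD of the difference in knee share between two arms = √(2 × 0.5 × 0.5 / 67) = 0.0864, or 8.6 points. The 95% range is 1.96 × 8.6 = ±17 points. A gap of at least 10 points has probability 26% for one pair of arms and 50% for the widest of the three pairs. For at least 15 points the figures are 7% and 17%.

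**Step 2: complications.** With knee share π, joint risks p₁ and p₂ and overall risk p, the part of the variance of the arm difference that stratifying can remove is π(1−π)(p₁−p₂)² / [p(1−p)]. For 10% v 5%: 0.25 × 0.05² / (0.075 × 0.925) = 0.9%.

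| Risks by joint (assumed) | Variance removed | SE of arm difference, crude → stratified (points) | Equivalent patients of 200 |
|---|---|---|---|
| 7.5% v 5% | 0.3% | 4.18 → 4.18 | 0.5 |
| 10% v 5% | 0.9% | 4.55 → 4.53 | 1.8 |
| 15% v 5% | 2.8% | 5.18 → 5.11 | 5.6 |
| 20% v 5% | 5.1% | 5.71 → 5.57 | 10.3 |
| 30% v 5% | 10.8% | 6.56 → 6.20 | 21.6 |

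A 15-point imbalance shifts the arm difference by 0.15 × 5 = 0.75 points (10% v 5%) or 0.15 × 15 = 2.25 points (20% v 5%), against SEs of 4.55 and 5.71.

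Simulation (200,000 runs per scenario, 67 per arm) compared the crude chi-squared test under unstratified allocation with a Mantel-Haenszel test under stratified allocation. Power at an assumed risk ratio of 0.3 was 28.0% v 27.7% (10% v 5%), 47.9% v 48.2% (20% v 5%) and 63.1% v 65.5% (30% v 5%). Type I error of the crude test under unstratified allocation stayed at 4.8% to 5.1%. With stratified allocation but a crude test, it fell to 4.3% (20% v 5%) and 3.6% (30% v 5%), so a stratified list should be matched by a stratified analysis.

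**Step 3: time and length-of-stay outcomes.** In a linear model, adjusting for joint leaves a fraction 1−R² of the variance, so 67 per arm acts like 67 / (1−R²). Power is for an assumed difference of 0.5 SD, two-sided 0.05; unadjusted it is 82%.

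| R² for joint (assumed) | Equivalent per arm | Power |
|---|---|---|
| 10% | 67 / 0.90 = 74 | 86% |
| 20% | 67 / 0.80 = 84 | 90% |
| 30% | 67 / 0.70 = 96 | 93% |

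At R² = 20% the two joints differ by √(0.20 / 0.25) = 0.894 SD. A 17-point imbalance then moves the arm difference by 0.169 × 0.894 = 0.15 SD, close to one standard error of √(2/67) = 0.17 SD.

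**The case against.** The strongest reply is that, on the primary endpoint, nothing is broken. Under random allocation the crude standard error already includes chance imbalance in joint, so the test is valid and stratifying gains little. That stands.

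Second, the plan is not without adjustment: a multivariate analysis is promised and procedural data are collected. That stands in part. A reader of the chi-squared and t-test sentence alone might infer that no adjusted analysis is planned, and section 5.2 does not support that. What is missing is the specification.

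Third, no document reports any outcome by joint. A reader might take joint to be an established predictor here. The documents do not show it, so every gain above depends on an assumed strength.

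Fourth, a broad population is a legitimate choice. Section 5.1 uses its hip and knee count for accrual only, so it does not show that section 2.4 is wrong or that other joints should be excluded.

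Finally, section 3.2 describes alternation, which is predictable. Alternating within joint would be just as predictable, and the imbalance figures above presume real randomisation. That is a separate and larger problem, which stratifying by joint does not solve.

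**Conclusion.** The point holds as a cheap improvement. Joint is pooled, is not an allocation stratum, and is not named in any analysis. For complications the effect is minor: about 0.3% to 5% of variance for risks up to 20% v 5%, rising to 10.8% only at 30% v 5%, with type I error preserved. For closure time, operative time and length of stay, adjustment is worth about 74 to 96 patients per arm instead of 67 if joint explains 10% to 30% of variance. These results rest on an assumed 50:50 mix, independent random allocation and assumed effects of joint.

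A reader might go further and infer that joint imbalance could use up a large part of the difference the trial is meant to detect. The documents do not support this: section 5.1 states no target difference, and the arm size at 80% power would fit gaps of about 16 to 19 points (21 − 5; 29 − 10).

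**What to change.** 1. In section 5.2, pre-specify joint (hip, knee, other) as a covariate in the models for closure time, operative time, length of stay and cost, in place of the unadjusted t-tests. Joint is known before surgery and can be recorded with the procedural characteristics already planned.
2. Report the complication comparison stratified by joint (Mantel-Haenszel), and state how it relates to the promised multivariate analysis.
3. Stratify the allocation list by joint. This is worth doing only once a genuine random list replaces the alternating method.

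Cost: one list per joint and one covariate. If complications are few, strata will be sparse, above all for joints other than hip and knee, and a stratum without events adds nothing to the stratified test. Section 2.4 can keep its eligibility; no patients need to be excluded.

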2.5 Exclusion Criteria

- Treatment of total joint replacement surgery at an outside institution
- Patients younger than 18
- Pregnant women, prisoners, adults unable to consent.

Vulnerable Subjects: No vulnerable subjects will be included within this study

CONFIDENTIAL

This material is the property of the NYU School of Medicine and Langone Medical Center. Do not disclose or use except as authorized in writing by the study sponsor

2.6 Subject Recruitment and Screening

All participants will be initially identified by participating surgeons among a large patient population scheduled for joint arthroplasty.

This study will be discussed with eligible patients by their surgeon at one of their pre-operative clinic visits. Research assistants working for the orthopaedics department will meet with patients during their pre-op visit to explain the study and obtain written informed consent using the IRB-approved consent form. A study log of consented patients will be maintained in a de-identified manner.

3 Study Treatment

